7.3 Criteria for Delay of Vaccination and/or Blood Sampling

Subjects may encounter clinical circumstances that warrant a delay in the administration of second trial vaccination at Day 90 (M3). These situations are listed below. In the event that a subject meets a criterion for delay of vaccination, the subject may receive trial vaccination once the window for delay has passed as long as the subject is otherwise eligible for trial participation. The decision to vaccinate in those situations will be made by the Investigator.

1. Body temperature $\geq 38.0^{\circ}\text{C}$ ($\geq 100.4^{\circ}\text{F}$) within 3 days of intended trial vaccination.
2. Receipt of any vaccine other than the trial vaccine within 14 days (for inactivated vaccines) or 28 days (for live vaccines) of intended trial vaccination.
3. Known or suspected altered or impaired immune function as specified under the exclusion criteria.

Criteria for contraindication to vaccination at Day 90 (M3):

There are also circumstances under which receipt of the second vaccination at Day 90 (M3) is contraindicated in this trial. These circumstances include but are not limited to anaphylaxis or severe hypersensitivity reactions following administration of the first vaccination at Day 1 (M0). If these reactions occur, the subject must not receive the second vaccination at Day 90 (M3), but will be encouraged to continue trial participation for safety follow up.

7.4 Criteria for Early Trial Termination of a Subject

Under some circumstances, a subject's trial participation may be terminated early. This means that no further trial procedures (including data collection) will be performed on that subject beyond the specific date of early termination. The primary reason for early termination of the subject's participation from the trial should be recorded in the eCRF "end of trial visit" page using the following categories. For screen failure subjects, refer to Section [9.1.10](#).

1. Adverse Event: The subject has experienced an AE (irrespective of being related/unrelated to the trial vaccine or trial-related procedures) that requires early termination because continued participation imposes an unacceptable risk to the subject's health and/or the subject is unwilling to continue participation because of the AE. If the subject is unwilling to continue because of the AE the primary reason for early termination in this case will be "withdrawal due to AE" and not "withdrawal of consent", see below. Any ongoing AEs leading to early termination should be followed by the Investigator until resolution or stabilization.
2. Lost to follow-up: The subject did not return to the clinic and at least 3 attempts to contact the subject (or subject's LAR) were unsuccessful. Attempts to contact the subject must be documented.
3. Withdrawal of consent: The subject (or subject's LAR) wishes to withdraw from the trial. The primary reason for early termination will be "withdrawal of consent" if the subject withdraws from participation due to a non-medical reason (ie, reason other than AE). The reason for withdrawal, if provided, should be recorded in the eCRF.

Note: All attempts should be made to determine the underlying reason for the withdrawal and, where possible, the primary underlying reason should be recorded.

4. Premature trial termination by Sponsor, a regulatory agency, the IEC/IRB, or any other authority.

If the clinical trial is prematurely terminated by the Sponsor, the Investigator is to promptly inform the trial subjects and local IEC/IRB and should assure appropriate follow up for the subjects. The primary reason for early termination in this case will be "trial termination".

5. Subject's death during trial participation.
6. Other.

Note: The specific reasons should be recorded in the "specify" field of the eCRF.

7.5 Criteria for Premature Discontinuation of Trial Vaccine Administration

Early termination of a subject's participation in the trial will by default prevent the subject from continued trial vaccine administration, as the subject will no longer be participating in the trial. In addition to early termination (see Section 7.4) criteria, other situations may apply in which subjects may continue participating in the trial (e.g., contributing safety data according to protocol) but trial vaccine administration is discontinued selectively. Regardless of the reasons for discontinuation of the trial vaccine administration, this must be documented as protocol deviation. Even if the subject is deemed ineligible to receive trial vaccine, all efforts should be made to continue the collection of safety data according to protocol. In addition, the primary reason for premature discontinuation of trial vaccine administration should be recorded in the eCRF ("end of trial vaccine administration" page) using the following categories:

1. Adverse Event: The subject has experienced an AE (irrespective of being related/unrelated to the trial vaccine or trial-related procedures) for which subsequent trial vaccine administrations impose an unacceptable risk to the subject's health, but the subject may continue trial participation for safety, or a subset of other trial procedures.
2. Lost to follow-up: The subject did not return to the clinic and at least 3 attempts to contact the subject (or subject's LAR) were unsuccessful. Attempts to contact the subject must be documented.
3. Withdrawal of consent: The subject (or subject's LAR) wishes to withdraw from the trial. The primary reason for early termination will be "withdrawal of consent" if the subject withdraws from participation due to a non-medical reason (i.e., reason other than AE). The reason for withdrawal, if provided, should be recorded in the eCRF.
4. Premature trial termination by the Sponsor, a regulatory agency, the IEC/IRB, or any other authority.

If the clinical trial is prematurely terminated by the Sponsor, the Investigator is to promptly inform the trial subjects and local IEC/IRB and should assure appropriate follow up for the subjects. The primary reason for early termination in this case will be "trial termination".

5. Subject's death during trial participation.
6. Protocol deviation: A protocol deviation is any change, divergence, or departure from the trial design or procedures of a trial protocol. The subject may remain in the trial unless continuation in the trial jeopardizes the subject's health, safety, or rights (see Section 7.4).
7. Pregnancy: Any subject who, despite the requirement for adequate contraception, becomes pregnant during the trial will not receive further trial vaccine administrations. Pregnant subjects should, however, be asked to continue participating in the trial contributing data to the safety follow-up according to protocol. In addition, the site should maintain contact with the pregnant subject and complete a "Clinical Trial Pregnancy Form" as soon as possible. The subject should be followed-up until the birth of the child, or spontaneous or voluntary termination; when pregnancy outcome information becomes available, the information

should be captured using the same form. Data obtained from the “Clinical Trial Pregnancy Form” will be captured in the safety database.

8. Receipt of any other dengue vaccines (investigational or licensed) during the trial.
9. Other

Note: The specific reasons should be recorded in the “specify” field of the eCRF.

8.0 CLINICAL TRIAL MATERIAL MANAGEMENT

This section contains information regarding all vaccines and materials provided directly by the Sponsor, and/or sourced by other means, that are required by the trial protocol, including important sections describing the management of clinical trial material.

8.1 Trial Vaccines and Materials

[figure not shown]
The investigational vaccine is TDV, a tetravalent dengue vaccine comprised of 1 molecularly characterized, attenuated dengue virus strain, and 3 chimeric dengue virus strains with potencies of not less than 3.3, 2.7, 4.0 and 4.5 \log_{10} plaque forming units per dose of TDV-1, TDV- 2, TDV-3, and TDV-4, respectively. TDV is a lyophilized vaccine that will be reconstituted in diluent (37 mM NaCl solution) prior to administration. The diluent will be presented in pre-filled syringes (PFS).

Placebo is normal saline solution (0.9% NaCl) for injection.

8.1.1 Dosage Form, Manufacturing, Packaging, and Labeling

TDV:

CC1

Placebo kits:

The placebo is normal saline for injection (0.9% NaCl). The placebo is presented in 2 mL single dose vials for 0.5 mL dosing. The units will be labeled with a single panel or booklet label that will contain pertinent trial information in local languages. The placebo dose is packaged into single dose dispensing cartons. The cartons will be labeled with a single panel or booklet label that will contain pertinent trial information in local languages.

8.1.2 Storage

The trial vaccines (TDV and placebo) and TDV diluent will be shipped in refrigerated containers at 2°C to 8°C. From receipt and prior to use, trial vaccines and TDV diluent must be protected from light and stored at 2°C to 8°C in a refrigerator.

All clinical trial material must be kept in an appropriate, limited-access, secure place until it is used or returned to the Sponsor or designee for destruction. All Sponsor-supplied vaccines must be stored under the conditions specified on the label, and remain in the original container until dispensed. A daily temperature log of the vaccine storage area must be maintained every working day. Temperature excursions must be reported to the Sponsor as soon as possible and use of these vaccines requires Sponsor approval.

8.1.3 Dose and Regimen

The trial vaccine doses that will be provided to each trial group are presented in [Table 8.a](#).

The trial vaccines will be prepared and administered by the unblinded pharmacist or vaccine administrator according to the instructions in the Pharmacy Manual or per Sponsor instructions.

Lyophilized TDV will be reconstituted by adding the entire content of the PFS with diluent to the vial containing TDV. Reconstituted TDV will appear as a clear, colorless to yellow solution essentially free of foreign particulate.

The placebo dose will appear as a clear, colorless solution essentially free of foreign particulate. TDV and placebo will be administered by the SC route.

Table 8.a Sponsor-Supplied Vaccine and Placebo

Group	Number of subjects	Day 1 (M0)	Day 90 (M3)
Group 1	300	TDV, SC	TDV, SC
Group 2	100	Placebo, SC	Placebo, SC

M=Month; SC=subcutaneous

8.2 Trial Vaccine Assignment and Dispensing Procedures

The vaccine to be used will be identifiable by a unique identification number and managed by interactive response technology (IRT). Refer to Section [8.6](#) for accountability of Sponsor-supplied vaccines.

The Investigator or designee will use the IRT at subject enrollment to obtain the subject number. This number will be used throughout the trial.

The Investigator or designee will use IRT on the day of first dosing (Day1 [M0]) to provide the necessary subject identifying information.

The Investigator or designee will use IRT at each dispensing visit to obtain the vaccination identification number for the vaccine dose.

The Investigator or designee will be responsible for overseeing the administration of vaccine to subjects enrolled in the trial according to the procedures stipulated in this trial protocol. The vaccine will be administered only by an unblinded site administrator or pharmacist who is qualified to perform that function under applicable laws and regulations for that specific trial.

If Sponsor-supplied vaccine is lost or damaged, the site can request a replacement. Expired vaccines must not be administered.

Prior to vaccination, a subject must be determined to be eligible for trial vaccination and it must be clinically appropriate in the judgment of the Investigator to vaccinate. Eligibility for vaccination prior to first trial vaccine administration is determined by evaluating the entry criteria outlined in this protocol (Section 7.1 and Section 7.2).

Eligibility for subsequent trial vaccination is determined by the criteria outlined in Section 7.3.

Trial vaccines should not be administered to individuals with known hypersensitivity to any component of the vaccines.

Standard immunization practices are to be observed and care should be taken to administer the injection subcutaneously. In addition, WHO recommendations to reduce anxiety and pain at the time of vaccination should be followed [14]. Before administering the vaccine, the vaccination site is to be disinfected with a skin disinfectant (e.g., 70% alcohol). Allow the skin to dry. DO NOT inject intravascularly.

As with all injectable vaccines, trained medical personnel and appropriate medical treatment should be readily available in case of anaphylactic reactions following vaccination. For example, epinephrine 1:1000, diphenhydramine, and/or other medications for treating anaphylaxis should be available.

8.3 Randomization Code Creation and Storage

Randomization personnel of the Sponsor or designee will generate the randomization schedules. Randomization information will be stored in a secured area, accessible only by authorized personnel.

8.4 Trial Vaccine Blind Maintenance

The trial will be conducted in a double-blind manner. The investigational vaccine blind will be maintained using IRT. The subjects, data collectors (eg, Investigator), and data evaluators (eg, trial statisticians) are blinded. One or more designated pharmacist's/vaccine administrators at the site will be unblinded. These unblinded designees will maintain the investigational vaccine blind and will have no role in the assessment of subject safety.

8.5 Unblinding Procedure

The trial vaccine blind shall not be broken by the Investigator unless information concerning the trial vaccine is necessary for the medical treatment of the subject. In the event of a medical emergency, if possible, the medical monitor should be contacted before the trial vaccine blind is broken to discuss the need for unblinding.

For unblinding a subject, the trial vaccine blind can be obtained by the Investigator, by accessing the IRT.

The Sponsor's Pharmacovigilance Department must be notified as soon as possible if the trial vaccine blind is broken by the Investigator and the completed SAE form must be sent within 24 hours. The date, time, and reason the blind is broken must be recorded in the source document and the same information (except the time) must be recorded on the eCRF.

If any subject is unblinded, no further doses of trial vaccine are to be administered and the subject must be withdrawn from the trial.

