2.1 Schedule of Trial Procedures

Visit number	V1	V2	V3	V4	V5 ^(a)
Day	Day	Day 30	Day 90	Day 120	Day 270
	1			(V3+30 days)	(V3+180 days)
Day	M0	M1	M3	M4	M9 (ET)
Visit window (days)	±0	-1/+7	-4/+7	-1/+7	-7/+14
Informed consent/assent ^(b)	X				
Assessment of eligibility criteria ^(c)	X				
Demographics	X				
Medical history	X				
Concomitant medications/vaccinations ^(d)	X	X	X	X	X
Check criteria for delay of trial vaccination	X		X		
Check contraindications to trial vaccination			X		
Complete physical examination ^(e)	X		X		
Targeted physical examination ^(f)		X		X	X
Vital signs ^(g)	X	X	X	X	X
Pregnancy test ^(h)	X		X		
Pregnancy avoidance guidance ⁽ⁱ⁾	X	X	X	X	
Randomization	X				
Blood sample for dengue neutralizing antibodies (5 mL) ^(j)	X			X	X
Trial dose administration ^(k)	X		X		
Injection site evaluation ^(l)	X		X		
Diary card ^(m)	Distribution	X		X	
	Review/collection		X		X
Unsolicited adverse events (AE) ⁽ⁿ⁾	X	X	X	X	
Serious adverse events (SAE) and AEs leading to subject discontinuation or withdrawal ^(o)	X	X	X	X	X
Medically attended AEs (MAAE) ^(o)	X	X	X	X	X

ET=Early Termination; M=month, V=visit

Footnotes:

- (a) If the subject terminates early, Day 270 (M9) procedures should be performed.
- (b) Up to 28 days prior to the day of randomization.
- (c) Review of inclusion/exclusion criteria will be performed prior to administration of the first trial dose at Day 1 (M0). After eligibility is assessed and written informed consent/assent has been obtained, subjects will be randomized to receive either 2 doses of TDV or placebo by subcutaneous (SC) injection.
- (d) Any other vaccination against any flavivirus (licensed or investigational, including any other dengue vaccine) during the entire trial period, all concomitant medications, vaccine history from 1 month (minimum 28 days) prior to administration of each trial dose of TDV or placebo up to 1 month (minimum 28 days) thereafter, steroids and immunostimulants within 60 days prior to Day 1 (M0), immunoglobulins and blood products within 3 months prior to Day 1 (M0), and immunosuppressive therapy within 6 months prior to Day 1 (M0).
- (e) Physical examination including measurement of vital signs (see footnote [g]), weight and height; body mass index (BMI) will be calculated automatically. Measurement of height is only required at Day 1 (M0).
- (f) Subjects may undergo a brief symptom-directed physical examination. Clinically significant changes from the Baseline

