9.1.9 Pregnancy

To ensure subject safety and the safety of the unborn child, each pregnancy in a subject having received a trial vaccine must be reported to the Sponsor within 24 hours of the site learning of its occurrence. If the subject becomes pregnant during the trial, she will not receive any further doses of any Sponsor-supplied trial vaccine. The pregnancy must be followed to determine

outcome, including spontaneous or voluntary termination, details of birth, and the presence or absence of any birth defects, congenital abnormalities, or maternal and/or newborn complications. This follow-up should occur even if the intended duration of safety follow-up for the trial has ended.

Any pregnancy occurring following trial dose administration should be reported immediately, using a pregnancy notification form, to the contact listed in the Investigator Site File.

The Investigator must inform the subject of their right to receive treatment information. If the subject (or subject's LAR) chooses to receive unblinded treatment information, the individual blind should be broken by the Investigator and procedures must be followed as described in Section 8.5.

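### Withdrawing every unblinded subject (Protocol 8.5) ends routine collection of new MAAEs and of new SAEs not thought vaccine-caused, most clearly for a pregnant subject who chooses unblinding

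*Protocol*

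**What the plan says.** Protocol 8.5 lets the investigator break the blind only for treatment; it is otherwise kept "unless information concerning the trial vaccine is necessary for the medical treatment of the subject". The consequence has no exceptions: "If any subject is unblinded, no further doses of trial vaccine are to be administered and the subject must be withdrawn from the trial".

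Protocol 7.4 defines what leaving the trial means for data: "no further trial procedures (including data collection) will be performed on that subject beyond the specific date of early termination".

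Pregnancy has its own route. Under Protocol 9.1.9 the investigator must tell the subject that she may learn her treatment. If she or her legal representative wants this, "the individual blind should be broken by the Investigator and procedures must be followed as described in Section 8.5". Protocol 7.5 item 7 says that pregnant subjects stop dosing but should "be asked to continue participating in the trial contributing data to the safety follow-up according to protocol".

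Two other places show what the protocol wants when only dosing stops. Section 7.5 says in general that "all efforts should be made to continue the collection of safety data according to protocol". Section 7.3 bars dose 2 after anaphylaxis or severe hypersensitivity to dose 1, "but will be encouraged to continue trial participation for safety follow up".

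The share of subjects with an MAAE or SAE over the whole trial is a secondary endpoint (Protocol 5.2.2). SAP 7.11.1 summarizes AEs after the first, the second and any vaccination, with Safety Set subjects given the dose concerned as the denominator.

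**The concern.** MAAEs are collected by interview at site visits (Protocol 10.4.3), and routine SAE collection is planned to Day 270 (10.4.4). A subject withdrawn under 8.5 has no further scheduled visits, so neither continues. The loss is imposed by the protocol, just after a medical event or a pregnancy, on someone who may be willing to stay.

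Pregnancy shows it most plainly. Of two pregnant subjects, the one who stays blinded is asked to remain in safety follow-up. The one who uses the right given in 9.1.9 is withdrawn. Nothing about her safety explains the difference.

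The whole-trial MAAE and SAE percentages are at stake, along with the completeness of safety data in a small group of particular interest. Withdrawn subjects stay in the Safety Set, so an event that nobody collects is tabulated as no event.

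**Working it through.** The plan gives no figure to reproduce. The check sets the sections side by side and then sizes the loss.

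**What stops and what survives after withdrawal**

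| Item | After withdrawal | Source |
|---|---|---|
| New MAAEs | Not collected | Protocol 7.4, 10.4.3 |
| New SAEs not thought vaccine-caused | Not routinely collected, apart from pregnancy follow-up | 7.4, 10.4.4 |
| New unsolicited AEs in an open 28-day window | Not collected | 7.4, 10.4.1 |
| Events up to the withdrawal date | Captured if the early-termination visit takes place | 2.1 footnote (a), 9.3.5 |
| Known AEs and SAEs | Followed | 7.4 item 1, 10.4.1, 10.5.1, 10.5.2 |
| SAE form within 24 hours of unblinding | Required | 8.5 |
| Pregnancy outcome, complications in mother or newborn | Followed whatever the cause | 9.1.9 |
| Later SAEs thought vaccine-caused | Reportable | 10.5.4 |

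On the early-termination visit the schedule says: "If the subject terminates early, Day 270 (M9) procedures should be performed". That visit looks back to withdrawal; it does not extend collection beyond it.

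**Collection time lost**

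Inputs: first dose at Day 1, last visit at Day 270, Visit 5 at Visit 3 + 180 days with window -7/+14 (Protocol 2.1). Withdrawal is assumed to fall on the day of unblinding. Nominal follow-up is 270 - 1 = 269 days.

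| Unblinded on | Days lost | Share of 269 days |
|---|---|---|
| Day 30 | 270 - 30 = 240 | 89.2% |
| Day 90 | 270 - 90 = 180 | 66.9% |
| Day 120 | 270 - 120 = 150 | 55.8% |

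With the Visit 5 window, the Day 90 figure becomes 180 - 7 = 173 to 180 + 14 = 194 days. A positive pregnancy test at Visit 3 is an example of the Day 90 case. The window for unsolicited AEs after dose 1 has closed by then. At worst, 27 days of such a window are lost, when unblinding falls on a vaccination day.

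**Effect on the percentages**

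Each subject counts once per table. One subject whose first event goes uncollected lowers the percentage by 100 × 1/N points:

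- Full planned enrolment: 1/300 = 0.33 points (TDV), 1/100 = 1.0 point (placebo).
- 90% dosed (assumed): 1/270 = 0.37 and 1/90 = 1.11 points.
- 80% dosed (assumed): 1/240 = 0.42 and 1/80 = 1.25 points.
- Subject who already has that type of event: 0.

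A subject unblinded before dose 2 is not in the second-vaccination denominator. The dilution then applies only to the first-vaccination and any-vaccination summaries.

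**Ceiling for a group**

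The documents give no unblinding rate. Take a common rate of 0.33% to 1% in both groups as an assumption. That is 1 to 3 of 300 TDV subjects and an expected 0.33 to 1 of 100 placebo subjects. If every one of them has a first event only after withdrawal, the percentage falls by the rate itself:

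- TDV: 1/300 to 3/300 = 0.33 to 1.0 points.
- Placebo: 0.33/100 to 1/100 = 0.33 to 1.0 points. In practice this group loses either nothing or 1.0 point, since subjects are whole.

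**The case against.** **Treatment-driven unblinding usually accompanies an SAE.** Section 8.5 requires an SAE form within 24 hours, which suggests that the authors expected this. Such a subject is already in the SAE numerator, so the effect on the SAE percentage is zero. This stands. It does not protect the MAAE percentage, because 10.1.3 defines MAAEs as non-serious. Nor does it help in the pregnancy route, since pregnancy itself is not among the seriousness criteria in 10.1.4.

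**Withdrawal keeps unblinded ratings out of the data.** Section 8.4 wants data collectors blinded, and an investigator who knows the assignment may rate severity and causality differently. The bias is real, but withdrawal does not supply blinded ratings in place of unblinded ones; it supplies none. The endpoint counts any MAAE or SAE, so the bias mainly touches the severity and related-event tables.

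**Every drop-out dilutes the percentage in this way.** True. SAP 7.7 shows follow-up duration by group, and SAP 7.3 shows the reasons for discontinuation. The difference is that here the protocol causes the drop-out.

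**Section 8.5 does not cite 7.4, and unblinding is not a listed 7.4 category.** Also true; it would fall under the residual category. Section 7.4 is nonetheless the only text that says what leaving means for data collection.

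A reader might infer that 7.3 and 7.5 contradict 8.5. The documents do not support this: neither mentions unblinding, and the general rule in 7.5 covers subjects who stop dosing but remain in the trial. They show an intent that 8.5 does not carry over. Even for pregnancy, the mandatory wording of 9.1.9 suggests that 8.5 prevails over the request in 7.5 item 7. A reader might also infer that all safety information is lost after unblinding; the list of what survives shows otherwise.

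**Conclusion.** The point holds in a limited form. Sections 8.5 and 7.4 together end routine collection of new MAAEs and of new SAEs not thought vaccine-caused for any unblinded subject. The pregnant subject who elects unblinding is the clearest case, because another section wants her asked to stay.

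The loss is large for the individual, about two thirds of nominal follow-up at Day 90, and small for the trial. Under the assumed common rate, neither percentage falls by more than about 0.33 to 1.0 points at full enrolment. The true number unblinded is probably small. A reader might infer a fall of up to 3.0 points for placebo by supposing three unblinded subjects in each group. That would need 3% of placebo subjects unblinded against 1% on TDV, each with a first event only after withdrawal. Nothing in the documents suggests such an imbalance under 3:1 allocation.

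The trial is descriptive, with no hypothesis test on these percentages, and the primary GMT analysis is not materially affected. The change is worth making because it is inexpensive and preserves safety data, not because a conclusion depends on it.

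**What to change.** - **Protocol 8.5:** keep the stop on further doses. Replace the withdrawal requirement with an instruction that the subject will be asked to continue SAE, MAAE and other scheduled safety follow-up to Day 270.
- **Protocol 9.1.9:** after the reference to 8.5, add that an unblinded pregnant subject is asked to continue safety follow-up under 7.5 item 7.
- **SAP 7.11.1:** flag AEs assessed after unblinding. No separate listing of unblinded subjects is needed: 8.5 already puts the date and reason on the eCRF, and SAP 7.1.1 already lists all collected data.

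Section 7.4 can stay as it is. The text changes are short and the visits are already scheduled. The change needs prior IRB/IEC approval (Protocol Appendix A item 5). It may also need a revised consent/assent form, which subjects or their representatives would have to sign again (15.2). The remaining downside is that severity and causality ratings after unblinding are not blinded; the flag makes that visible but does not remove it.
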